In the second part of the study we will enroll from 60 to 70 serodiscordant couples. All HIV serodiscordant couples entering the second part of the study will be administered a baseline, 6-, 12-, and 18-month survey. We will collect ongoing clinical data from each clinic visit, and from the larger clinic population for comparison. Positive partners engaged in care as a dyad will have a viral load test at 18-months. Biometric data (fingerprint) will be collected at study and intervention encounters to link utilization of services with survey data. We will also enroll serodiscordant couples from patients already receiving care from the Kisarawe Care and Treatment Center (CTC). To ensure serodiscordant couples who participated in the self-testing phase have an opportunity to enroll in the second part of the study, we will keep enrollment open until approximately 1-month after the target enrollment for the second part of the study is reached. Based on historical rates of serodiscordant status among couples we estimate that we will need to enroll approximately 442 couples to identify 60 couples for the second part of the study, however, it may take up 1000 couples in the first part of the study to find this many serodiscordant couples. Additionally, since we will be conducting the HIV self-testing by geographic cluster, we will offer HIV self-testing to all eligible persons in each cluster that we start to avoid denying people in the geographic clusters access to HIV self-testing and also biasing our sample. This may result in us completing the enrollment of the 60 couples for the second stage of the project while still providing HIV self-testing in the first stage of the study. Thus, we may need to exceed the N of 60 as we complete the final geographic cluster with HIV self-testing to assure that those found to be discordant through self-testing have an opportunity to engage in the second part of the study. We thus may have up to 70 couples enrolled in the second part of the study. Because of the diversity in recruitment strategies, we will be able to track uptake of care between those newly diagnosed with HIV and those with previous diagnoses who have already begun receiving care.

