Sampling of Households –Based on data from the 2012 census, Kisarawe Ward will be divided into sections by village and sub-village. To begin sampling, one village/sub-village will be selected. Once selected, data collectors will visit every household in the selected area. Once an entire section has been covered, data collectors will select a new section of the ward to sample. This process will continue until approximately 442 couples have been enrolled, although we may need to enroll up to 1000 couples as described earlier. To recruit for the second component of the study we will approach couples who participated in self-testing and are found to be serodiscordant. We will also recruit the serodiscordant cohort from patients already enrolled in care at the Kisarawe CTC. We will continue recruiting using both methods until 60 serodiscordant couples (but up to 70 as described earlier) have enrolled in the second part of the study. We may recruit more than 442 couples—but no more than 1,000 couples—in the self-testing component of the study in order to enroll 60 serodiscordant couples in the second part of the study. As well, we may enroll up to 70 serodiscordant couples in the second part of the study if we are continuing to finish out a geographic cluster with provision of HIV self-testing.

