Data Structure: There are two key unique features of the primary data for this proposal. First, because couples are enrolled in the study, there is inherent nesting of two individuals within each couple. Second, the measurement design leads to repeated measurements outcomes for some of the aims. Given the aims of the study, many of the outcomes will be evaluated using descriptive statistics. However, issues such as nesting and repeated measurements will be carefully considered. For example, for the first aim, uptake will be reported by each individual within the couple, and the descriptive statistics will be reported both at the individual level within the couple and at the aggregate couple level. For the outcomes that will be evaluated using inferential statistical analyses, the nested data structures (e.g., repeated measurements within couples) will be addressed using mixed-effects regression models (MRMs; e.g.).⁸¹ These highly flexible models accommodate variability in the number/spacing of outcome measurements, and they readily accommodate linear and non-linear outcome distributions (e.g., dichotomous, count). **Outcome Distributions & Individual Trajectories:** Prior to analysis, each outcome will be carefully inspected to determine the most appropriate distribution for modeling. Likewise, for outcomes with repeated measurements, the trajectory for each participant on each outcome will be plotted using “spaghetti plots”.⁸² These plots will illustrate the level of and variability in each outcome, along with patterns of change over time. **Model Building & Estimation:** Singer and Willett’s (2003)⁸³ model building approach will be used to specify fixed and random effects. The MRMs will be performed using MLwiN software.⁸⁴ Due to the relatively modest sample size for some of the analyses, the models will also be performed using Bayesian MCMC-based estimation⁸⁵ in MLwiN. This simulation-based approach utilizes a large number of iterations – each informing the next – to produce an empirically-based sampling distribution for each parameter. For example, rather than a single point estimate of the parameter of interest, the MCMC-based provides the magnitude, precision, and variability of the parameter estimates. **Attrition & Missing Data:** Individuals or couples who drop out of clinic care will be retained, when possible, in ongoing research measurement according to Intention-to-treat principles.⁸⁶ Some research data will inevitably be missing, and the methods recommended by Schafer and Graham⁸⁷ will be used to evaluate missing data assumptions and guide the subsequent analyses. Given few missing data and evidence supporting a MAR mechanism, the procedures detailed above will be utilized with all available data. Given non-trivial missing data and evidence supporting MAR, multiple imputation for longitudinal data will be used to provide complete data.⁸⁸ Finally, given non-trivial missing data and evidence suggesting NMAR, pattern mixture models will be used to control the missing data.⁸²

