Precision of Estimates and Statistical Power: The level of precision and statistical power is necessarily limited given the stage of the research and the sample size associated with many of the outcomes. For the descriptive statistics, the margin of error was computed as an indicator of the level of precision afforded by the sample.

For AIM 1 – Based on our review of available literature on the prevalence of HIV sero-discordancy in stable couples we estimate that we will need to enroll approximately 442 couples to yield enough serodiscordant couples (N=60) to enroll in the second phase of the study. However, this is an uncertain estimate, and it may require up to 1000 couples. The expected percentage of the sample that will opt to use the HIV self-test is 50%-70%. The widest margin occurs at the level of 50%; therefore, this value was selected. With a sample of 442 and self-test use of 50%, the 95% confidence interval for the true value of this estimate is 46% to 54%. With a sample of 1000 and self-test use of 50%, the 95% confidence interval for the true value of this estimate is 48% to 52%.

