Year 1: Obtain IRB approval from MUHAS and MUSC; finalize survey; hire and train data collection staff; conduct household mapping and validate GIS data; prepare communities for study. Year 2: Hire and train locally based intervention staff; Collect baseline data. Year 3: Implement Intervention. Track participants. Collect quality assurance data. Collect clinical and cost data. Year 4: Track participants. Collect quality assurance data. Collect clinical and cost data. Draft manuscripts for publication. Year 5: Track participants. Complete collection of behavioral, biological, clinical, and cost data. Complete quality assurance on data; conduct data analyses; draft manuscripts for publication.

E. PROTECTION OF HUMAN SUBJECTS

Human Subjects Involvement and Characteristics

An individual's decision to participate in the cohort will not affect his or her ability to utilize standard of care HIV prevention services or treatment offered in the area.

We will seek to enroll between 442 couples and 1,000 couples in the cohort to assess the study outcomes from a community with population of approximately 11,900. As noted earlier, we may need to recruit more than 442 couples, up to a maximum of 1,000 couples, in order to meet the enrollment criteria of 60 serodiscordant couples in the second portion of the study. In addition, we may enroll up to 70 couples for the second part of the study as we complete the provision of HIV self-testing in the final geographic cluster getting HIV self-testing (as we need to complete the entire cluster for the voracity of the study sampling). The cohort of this size is calibrated to meet our specific aims of determining the uptake of HIV self-testing, self-referral for care when infected, engagement in care, retention in care, and the safety and acceptability of the intervention. Pregnant women and children age 18-21 years will not be excluded from seeking HIV prevention services or from participating in the self-testing cohort.

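### The Aim 1 uptake intervals are narrower than even a simple random sample of couples allows, and enrolment by whole sections of the ward is left out of the precision statement and the uptake model

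*Combined protocol and SAP*

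**What the plan says.** Sampling of Households divides Kisarawe Ward by village and sub-village. "To begin sampling, one village/sub-village will be selected". The team is to call at all homes there before moving on, and the rule for moving on reads: "Once an entire section has been covered, data collectors will select a new section of the ward to sample". Enrolment goes on in this way until about 442 couples, and at most 1,000, have joined. How the first or any later section is picked is not stated.

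The opening summary says that, "since we will be conducting the HIV self-testing by geographic cluster", kits go to everyone eligible in any section that is started, partly to avoid a biased sample. Human Subjects Involvement and Characteristics adds that "we need to complete the entire cluster for the voracity of the study sampling".

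In the Analysis Plan, the Data Structure paragraph begins "There are two key unique features of the primary data for this proposal". The two are partners within couples and repeated measurements; no geographic level is named. Uptake is to be described for individuals and for couples. The Aim 1 uptake regression is a single-level logistic model, with age and gender as example predictors.

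Precision of Estimates and Statistical Power takes 50% uptake as the widest case. At 442, it says "the 95% confidence interval for the true value of this estimate is 46% to 54" per cent; at 1,000, the interval is 48% to 52%. It gives no design effect, ICC, number of sections or finite population correction.

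**The concern.** Two separate things look wrong. First, the stated intervals are tighter than the usual formula gives for those sample sizes. Second, neighbours may resemble each other in past testing, access and local talk about HIV. A sample built from whole sections can then carry less information than its count of couples suggests.

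The single-level model treats its rows as independent. Gender is a predictor, so the rows must be individuals, and the model also omits the couple nesting that Data Structure says will be considered. The Intervention section makes that nesting matter: kits are given only if both partners agree, so partners' outcomes are linked.

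At stake are the uptake proportion, for which the hypothesis is a majority, and the odds-ratio intervals on which the regression results are to focus.

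**Working it through.** **Inputs from the plan:** p = 50%; n = 442 and 1,000 couples; 95% level; 3,101 households in the ward (Community Selection). **Inputs not in the plan, so assumed:** couples per section m = 15 to 55; ICC = 0.01 to 0.05.

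**1. Check the formula on the plan's own figures.** Half-width = 1.96 × √(p(1−p)/n). For the PrEP outcome with n = 50:
- p = 50%: 1.96 × √(0.25/50) = 13.9 points, giving 36–64%, as stated.
- p = 75%: 1.96 × √(0.1875/50) = 12.0 points, giving 63–87%, as stated.

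**2. Apply it to Aim 1.**
- n = 442: 1.96 × √(0.25/442) = 4.66 points, giving 45.3–54.7% (stated 46–54%).
- n = 1,000: 1.96 × √(0.25/1000) = 3.10 points, giving 46.9–53.1% (stated 48–52%).

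Rounding does not explain the gap: whole percentages would be 45–55% and 47–53%. Wilson, exact and Agresti-Coull limits agree within 0.1 point. A half-width of 4 points needs 0.25 × (1.96/0.04)² ≈ 600 independent couples; 2 points needs 0.25 × (1.96/0.02)² = 2,401.

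**3. Try other simple readings.** A 90% interval matches the first figure (46.1–53.9%) but not the second (47.4–52.6%). Independent individuals match the second (2,000: 47.8–52.2%) but not the first (884: 46.7–53.3%).

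**4. Add clustering by section.** Design effect = 1 + (m − 1) × ICC; the half-width is multiplied by its square root. Every household in a section is visited and further sections are then added. Section size therefore stays the same and the number of sections grows with n.

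| m | ICC | Design effect | Half-width, n = 442 | Half-width, n = 1,000 |
|---|---|---|---|---|
| 15 | 0.01 | 1 + 14 × 0.01 = 1.14 | 4.66 × √1.14 = 5.0 | 3.10 × √1.14 = 3.3 |
| 55 | 0.05 | 1 + 54 × 0.05 = 3.70 | 4.66 × √3.70 = 9.0 | 3.10 × √3.70 = 6.0 |

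At 442 couples these section sizes imply about 29 sections (442/15) down to 8 (442/55).

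**5. Effect of a finite population correction.** The factor is √((N − n)/(N − 1)). As an illustration, assume m = 50, ICC = 0.02 (design effect 1.98) and N = 2,000 eligible couples:
- n = 442: 4.66 × √1.98 × √(1558/1999) = 5.8 points.
- n = 1,000: 3.10 × √1.98 × √(1000/1999) = 3.1 points.

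Both remain wider than the stated 4 and 2.

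**6. What it could change.** Suppose 55% of 442 couples test. The simple-random-sample lower limit is 55 − 1.96 × √(0.55 × 0.45/442) × 100 = 55 − 4.64 = 50.4%. A design effect above (5/4.64)² ≈ 1.16 takes it below 50%.

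**The case against.** **The stated intervals might rest on an unstated method.** This is the strongest counter-argument. With no clustering, a finite population correction reproduces both figures after rounding if the ward holds about 1,306 to 2,861 eligible couples. So does counting individuals with a within-couple correlation of, say, 0.2: 1.96 × √(0.25 × 1.2/884) = 3.6 points and 1.96 × √(0.25 × 1.2/2000) = 2.4 points. However, the plan words its samples as 442 and 1,000 and mentions no correction, eligible-couple count or correlation. Taking all 3,101 households as N gives 4.32 and 2.55 points, so the second figure still fails. The finite-population argument does stand in part: if inference is limited to the ward, clustering costs less as coverage rises.

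**The study is exploratory.** The plan says precision is limited, and its majority hypothesis is approximate, with no decision rule tied to interval width. That limits the consequence but does not make the figures right.

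The documents do not support four stronger readings that a reader might infer:
- *Sections were chosen non-randomly or for convenience.* The method is simply unstated. Completing whole sections is a stated guard against bias, and Quality Assurance & Quality Control requires at least three household visits.
- *Starting near the Study Center would bias uptake.* Kits are delivered and explained at home, so using one needs no travel. An effect on linkage is conceivable but conjectural, since confirmatory testing is also offered at the two-week return.
- *Design effects reach about 7 at 1,000 couples.* Keeping 8 sections gives 125 couples each and 1 + 124 × 0.05 = 7.2, a half-width of 8.3 points. The sampling rule adds sections instead of enlarging them.
- *The whole gap from the stated 2 points is clustering.* About 1.1 points (3.1 − 2) is the arithmetic discrepancy. The comparator for clustering is 3.1.

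**Conclusion.** The point holds in two parts of different strength.

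The firm part is arithmetic. For samples of 442 and 1,000 couples, the stated half-widths of 4 and 2 points should be 4.7 and 3.1. This needs no assumption beyond the formula that the plan's own PrEP intervals follow.

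The second part is an omission whose size is uncertain. The plan describes sampling by whole sections but carries no section level into the Aim 1 intervals or model, and the model also drops the couple level. Any positive ICC makes the uptake interval too narrow relative to the simple-random-sample figure. Odds-ratio intervals are likely too narrow as well, most of all for characteristics that vary between sections. For a predictor that varies within couples, such as gender, ignoring the pairing can err the other way. Half-widths of 5.0–9.0 points at 442 couples and 3.3–6.0 at 1,000 rest on the assumed section sizes and ICCs and come before any finite population correction.

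Whether the covered sections represent the ward cannot be judged from the documents.

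**What to change.** 1. In Precision of Estimates and Statistical Power, restate the Aim 1 intervals as 45.3–54.7% (n = 442) and 46.9–53.1% (n = 1,000). Add design-effect-adjusted intervals over a stated ICC range, and state any finite population correction with the eligible-couple count it uses.
2. For the Aim 1 proportions and uptake regression, replace the single-level analysis with one that accounts for section, by a random effect or cluster-robust standard errors with a correction for a small number of sections. Account for couple as well whenever individuals are analysed.
3. Report how sections were chosen, how many there were and which were covered. Use a random order only for sections not yet started. The COVID-19 guidelines report 13 seronegative participants still enrolled at Tanzania's first confirmed case, so section selection has probably finished and a random draw before fieldwork appears too late.

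The cost is wider stated intervals, some SAP wording and slightly more analysis work.

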Enumeration of Household Members – When a household is approached for potential participation in the study, data collectors will explain the study, and with verbal consent of the head of household, establish if there are eligible couples within the household. Recruitment and Data Collection - Couples selected for inclusion will be invited to participate in the study. Couples are defined as two persons in an ongoing sexual relationship of at least 6-months, and each of these persons considers the other to be a “partner” in the relationship. To be eligible for participation, each individual has to be 18 years or older, live in the household regularly (thus, we are focused on cohabitating couples), and with no plans for moving from the area before the follow up period. Both members of the couple need to be aged 18 years or above, and at least one member of the couple must be aged 55 years or below. Additionally, each member of the couple must be willing to disclose their HIV status to their partner following self-testing, either facilitated by a counselor by the couples themselves. Before beginning the consent process, the interviewer will verify eligibility with the individual with respect to residency and age information. If the selected individual is not available during the household visit, the interviewer will be required to return to the household a minimum of two times (on different days/times of day) to locate the selected individual, request consent, and conduct the interview. Each member of eligible couples will be consented separately and in private, and consent of both members is required for entry into the study. Privacy will be ensured by having the consent and interview take place in a location where conversations cannot be overheard and the participant feels comfortable. If a couple declines to participate, they will be asked if they would be willing to tell us why. They will be consented for this process. At two weeks after leaving the self-testing kits with couples, data collectors shall return to study cohort members and repeat data collection (survey & blood for follow up interview). At this time, data collectors will collect any unused test kits and will also collect used test kits (sealable envelopes will be provided to participants to keep test kits after use). All collected test kits will be taken to the Study Center and kept in designated biohazard bins before being incinerated at the collaborating government health facility adjacent to the Study Center. At six months, a subset of participants will be approached to complete a follow up survey. The subset will consist of 50% of participants who were confirmed HIV positive (but no less than 20) and 5% of participants who tested negative (but no less than 10). For recruitment at the CTC, we will raise awareness about the study with existing CTC patients. If interested, these patients will be provided a card they can give to their partners to come and receive HIV testing through the study. The patients themselves will not have to retest for HIV since they are already receiving HIV-related care. The negative partner will receive HIV confirmatory testing at the Study Center. Serodiscordant couples in the area found through this recruitment strategy will be offered participation in the study. Similar eligibility criteria and definition of a “couple” used for the self-testing recruitment will also be used for the CTC-based recruitment (with the addition of residing near or within Kisarawe Ward). For CTC-based recruitment, written informed consent from both partners, completed individually and in private, will be required for entry into the study.

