measures were developed for Project Accept and will be used in this study. We will inquire about behavioral intention to seek VCT, attitudes (fears, worries, resolve, anxiety), self-efficacy to seek VCT, perceptions of abilities to overcome barriers, norms regarding VCT in the community, and perceptions of support for intentions. Items were constructed, tested for meaning in pilot studies, revised and translated/back-translated for meaning in Project Accept. In Project Accept these measures resulted in an alpha of 0.81 at baseline. **(5) Discussions about HIV** In the NIMH Collaborative HIV/STD Prevention Trial baseline questionnaire, questions were developed for a five-country community-randomized trial (Zimbabwe, Peru, China, India, and Russia) to capture key elements of community conversations about HIV/AIDS and the frequency of discussion with specific individuals (spouse, family, friends, key opinion leaders); we adapted these items for use. In Project Accept these measures resulted in an alpha of 0.76 at baseline. **(6) Disclosure of HIV status** will be measured as it was in earlier VCT research in Africa.⁷⁶ The instrument asks about the disclosure of serostatus to spouses, sexual partners, immediate family, other relatives, friends, religious leaders, health care professionals, and employers. The proportion of participants reporting each disclosure will be calculated after eliminating those who say the disclosure was not applicable to them. In Project Accept these measures resulted in an alpha of 0.83 at baseline. **(7) HIV-related negative life events** will be measured as they were in prior VCT research in Africa⁷⁶. Negative HIV-related life events include breakup of a marriage or sexual relationship, physical abuse by a sexual partner, neglect by family, being disowned by family, rejection by peers, and being discriminated against by health care providers or employers. The proportion of participants reporting each life event is calculated after eliminating those who say the life event was not applicable to them. In Project Accept these measures resulted in an alpha of 0.74 at baseline. **(8) Safety Related to Intervention** measures will assess specifically whether any adverse events (such as those listed in item 7 above) were experienced as an outcome of receiving each specific intervention component from the study. We will especially assess consequences of HIV self-testing, disclosure of HIV test results, accessing treatment, and PrEP utilization. We will also ask whether there was any coercion, pressure, or sanction for experience for clients to receive services and the source of each. These detailed questions will be added to our utilization data collection forms for each service assessing negative life events experienced from previous services received from the project. **(9) Potential for Misrepresentation** will also be assessed with regard to whether clients indicate higher risk behaviors than are true. We will do this by comparing data across couples, and over time to establish whether there are inconsistent results emerging. **(10) Cost** - The PI has significant experience with costing and cost-effectiveness analysis and led the costing component of the previous multi-site study. Cost data will include a range of costs for each item, with high, low, and average costs recorded. Data to be collected include: (1) Conversion rate of local currency to US dollars at 6-month intervals over the life of the project; (2) buying power of the currency at the beginning, midpoint, and end of the project based on the World Bank's Purchasing Power Parity Index; (3) costs of all commodities used in the intervention; (4) labor costs for intervention workers; (5) promotional and advertising costs; (6) average time clients spent with intervention; (7) rent; (8) maintenance; (9) incentives to participants; (10) volunteer activities; (11) user fees; (12) value of donated goods and services; and (13) other relevant costs. An annuity function will be applied to startup costs and they will be distributed over the life of the intervention. Time preference will be taken into account by applying discounting to future benefits at 0%, 5% and 7% as recommended by the US Panel on Cost-Effectiveness in Health and Medicine⁸⁰. **(12) Clinical** - for serodiscordant couples we will collect from the CTC: (1) date, time and reason for clinic visit, (2) results of CD4 and viral load tests (if any), (3) any reported medication side-effects, (4) medications prescribed, (5) pick up time and date of prescriptions, (6) HIV test results, (7) change or stop events for medications and associated reasons noted in record. These same results will be available in blinded format for other clients enrolled in the CTC and will be collected for comparison. In addition, for those in the cohort we shall conduct a HIV test at the follow up interview with counseling and referrals for care. For HIV positive members of serodiscordant couples followed in the cohort we will also collect blood for a viral load test at the time of the final interview to assess viral suppression.

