
Evaluation of Specific Aims & Associated Hypotheses

AIM 1 - We hypothesize that the majority of couples (GT ~ 50%) will utilize the HIV self-test kits and share their results with their partner. To evaluate the factors associated with uptake of HIV self-testing, a single level logistic regression model with a logit link function will be performed. The outcome will be the HIV self-testing status (0 = did not use self-test, 1 = used self-test). Demographic variables (e.g., age & gender) will be evaluated as predictors of self-testing uptake, with results focusing on ORs, and corresponding 95% CIs.

AIM 2 - We hypothesize that a large proportion of serodiscordant couples who present to the study referral office (GT ~ 70%) will engage in care together, have higher rates of adherence and retention than individually enrolled clients, and have a reduction in risk behaviors for HIV transmission from baseline to 18-month follow up. For this aim, there are repeated measurements of retention in care and adherence (level-1) nested within positive partners (level-2). A dichotomous predictor variable at the individual level (i.e., level-2) will test for differences in the log-odds of treatment retention between those enrolled in care as a couple and those enrolled in routine clinic services. The adherence outcome will be analyzed in a similar manner. For this outcome, there are several indicators of medication adherence. First, for the positive member of the couples, self-reports of ARV adherence will be obtained at 6, 12, and 18 months. Second, individuals on ARV are expected to return to the clinic each month to have the prescription refilled. Third, for individuals in the study, viral load tests will be obtained at 18 months allowing us to assess viral suppression as a marker for medication adherence. For the

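### Aim 1 self-test uptake rests on participants' own reports, and the protocol describes no use of the kits collected at the same visit to check them

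*Combined protocol and SAP*

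**What the plan says.** - **Source of the outcome.** In the Analysis Plan, under Data Structure, the Aim 1 example is that "uptake will be reported by each individual within the couple", summarised for individuals and for couples.
- **Coding.** Under Evaluation of Specific Aims, AIM 1: "The outcome will be the HIV self-testing status (0 = did not use self-test, 1 = used self-test". No source of the data is named there.
- **Hypothesis.** AIM 1 expects that "the majority of couples (GT ~ 50%) will utilize the HIV self-test kits and share their results with their partner". The precision section plans on uptake between 50% and 70%.
- **Kits.** The Recruitment and Data Collection text has staff return two weeks after leaving the kits, repeat the survey, and pick up unused kits as well as used kits in envelopes. Then: "All collected test kits will be taken to the Study Center and kept in designated biohazard bins before being incinerated". No counting, logging or linking step is described.
- **Disposal routes.** The Intervention section gives each couple two kits. It also lets participants dispose of a used kit themselves or bring it to the Study Center.
- **Misrepresentation check.** Measures item (9) compares partners' answers and answers over time, but its stated target is "whether clients indicate higher risk behaviors than are true", not claimed testing.

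**The concern.** Kits are handed over only if both partners agree to test and to disclose, and willingness to disclose is an eligibility condition. At week 2 a non-user must tell study staff that an agreed step was not taken, so some over-claiming is plausible. A returned unused kit would contradict such a claim, and staff already have that kit in hand. Once it is incinerated the check is lost unless its status was recorded.

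The plan asks for more elsewhere. In Aim 2, self-reported ARV adherence is supported by monthly refill records and an 18-month viral load. Aim 1 has no comparable support, although uptake of self-testing is among the study's main descriptive results.

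**Working it through.** **1. The plan's own precision figure.** At 50% use and n = 442 the plan states that "the 95% confidence interval for the true value of this estimate is 46% to 54" (per cent); at n = 1000 it states 48% to 52%. Using p ± 1.96 × √(p(1−p)/n):
- n = 442: 1.96 × √(0.25/442) = 4.7 points, giving 45.3% to 54.7%.
- n = 1000: 1.96 × √(0.25/1000) = 3.1 points, giving 46.9% to 53.1%.

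The stated limits are narrower by about 0.7 and 1.1 points per side. That is a separate matter. What matters here is that these intervals cover sampling error only.

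**2. Misreporting model.** Let p be true use, f the share of non-users who claim use, and u the share of users who deny it. Then observed = p(1−u) + (1−p)f. The documents give neither f nor u; the ranges f = 0-20% and u = 0-10% are assumptions.

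At true use of 50%:

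| f | u | Calculation | Observed |
|---|---|---|---|
| 0 | 10% | 0.50×0.90 + 0 | 45.0% |
| 5% | 10% | 0.45 + 0.025 | 47.5% |
| 5% | 5% | 0.475 + 0.025 | 50.0% |
| 10% | 0 | 0.50 + 0.05 | 55.0% |
| 20% | 0 | 0.50 + 0.10 | 60.0% |

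The bias can be positive, zero or negative. A larger sample does not reduce it: at f = 10%, u = 0 it is 5 points at either sample size.

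**3. When the comparison with 50% changes.** With u = 0, the over-report that lifts the observed figure to 50% is f = (0.50−p)/(1−p):
- true 40%: 0.10/0.60 = 16.7%
- true 45%: 0.05/0.55 = 9.1%
- true 48%: 0.02/0.52 = 3.8%

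With u = 5% the numerator becomes 0.50 − 0.95p, and the required f rises to 20.0%, 13.2% and 8.5%.

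Exact binomial results at n = 442, true use 48%, u = 0:

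| f | Chance observed exceeds 50% | Chance lower 95% limit exceeds 50% |
|---|---|---|
| 0 | 0.19 | 0.003 |
| 5% | 0.58 | 0.045 |
| 10% | 0.90 | 0.27 |

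At true use of 60% or 70% the lowest observed values in the assumed range are 0.60×0.90 = 54% and 0.70×0.90 = 63%, so the comparison with 50% does not change.

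**4. What the kits can show.** With two kits per couple, k unused kits returned means that at most 2−k partners used one. Any claims beyond that number are contradicted. A kit that is not returned shows nothing, because self-disposal is allowed. A used-kit envelope supports a claim but, left unopened, does not prove it.

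**The case against.** Several stronger conclusions are tempting, and the documents do not support them.

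- **That uptake will be overstated.** No misreporting rate is given, and step 2 shows that under-report can cancel or reverse the bias. Denial of use is conceivable: the protocol lists breakup, violence and discrimination among the risks of testing.
- **That 50% is a decision threshold.** It is a hypothesis in a study described as exploratory and proof of concept, and no action depends on it. Even an observed 50.5% with a 4.7-point half-width spans 45.8% to 55.2% and would not establish a majority.
- **That kit status is not recorded.** The text is silent, but the instruments are appendices outside the text available here, and Measures item (3) mentions ongoing data on testing utilization. A return field may exist. The Data Structure sentence is also mainly an illustration of nesting within couples.
- **That misreporting distorts the age and gender effects.** It could, but the documents give no basis for a difference between groups.

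Two further objections have force. The hypothesis concerns couples and requires sharing as well as use. If couple uptake needs both partners to report use, a couple in which neither tested is misclassified only if both over-claim: 0.10 × 0.10 = 1% at f = 10%, if their reports are independent. The person-level rates above therefore do not carry over directly to couples. Secondly, person-specific labels on used tests in a shared home could let one partner attribute a result to the other, and the protocol's risk section names loss of confidentiality.

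What remains is that no described step uses the kits, although a returned unused kit is direct contrary evidence.

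**Conclusion.** The point holds as a measurement weakness with a cheap, partial remedy. As written, Aim 1 uptake is self-reported, and a claim contradicted by a returned unused kit could still count as use. Uptake may be misstated, more plausibly upwards given the prior agreement to test and disclose. The size is unknown: under the assumed ranges, true 50% could appear as 45% to 60%. Whether a majority is claimed wrongly is in doubt only if true uptake is near or below 50%, the bottom of the planned range. It does not invalidate Aim 1, and the documents do not show that uptake will be overstated.

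**What to change.** **Record.** At the week-2 visit, or when kits are brought to the Study Center, enter on the tablet for each couple, before disposal, the number of kits returned unused, returned in a used-kit envelope, and not returned. Do not open envelopes or read results. Link a kit to a person only by a non-identifying code or by asking each partner privately at collection.

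**Analyse.**
- Keep self-reported uptake as the main outcome and label it as self-reported.
- Report its agreement with kit returns.
- Add a sensitivity analysis that counts claims contradicted by a returned unused kit as non-use.
- Treat claims with no returned kit as unverified, and bound uptake by counting them all as non-use (low) and all as use (high).

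**If collection is finished.** The COVID-19 section, which mentions 13 seronegative participants still enrolled and PrEP visits through early August 2020, suggests that it is. In that case use any existing return records. Otherwise report misclassification bounds from true = (observed − f)/(1 − f − u). For example, an observed 60% gives (0.60−0.20)/0.80 = 50.0% at f = 20%, u = 0, and 0.60/0.90 = 66.7% at f = 0, u = 10%.

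**Cost.** A few tablet fields at an existing visit, plus brief staff training on privacy. Verification is partial and gives an interval, and it cannot confirm the sharing-of-results part of the hypothesis.
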